### 9.5.1.2 Missing Data

Unless otherwise specified, missing data will not be imputed. For the derivation of new variables the following rules will apply:

Incomplete AE-related dates will be handled as follows:

- In case the onset date is completely missing or the onset is in the same year (if the onset year is available only) or the onset is in the same month and year (if the day is missing) as start of study treatment then the onset date will be replaced by the minimum of start of study treatment and AE resolution date.
- In all other cases the missing onset day or onset month will be replaced by 1.
- Incomplete stop dates will be replaced by the last day of the month (if day is missing only), if not resulting in a date later than the date of subject's death. In the latter case, the date of death will be used to impute the incomplete stop date.
- In all other cases the incomplete stop date will not be imputed.

For imputing missing parts of dates for the efficacy analyses the missing day in a date will be imputed as the 15th of the month, if month and year is documented. This includes also dates of start of follow-up therapy. In all other cases missing or incomplete dates will not be imputed if not indicated otherwise.

In individual subject data listings the documented date as given in the eCRF will be reported (e.g., \_\_May 2013 in case of day missing, but month and year available). No imputed values will be presented in clinical trial report. In all other subject data listings, imputed values will be presented. In those listings imputed date of death, last date known to be alive, start of AE, and relationship of AE to study treatment will be flagged.

## 9.5.2 Analysis of Primary Endpoints

### 9.5.2.1 Statistical Analysis of the Dose Escalation Cohort

The DLT Analysis Set will be used for evaluation of the number of subjects experiencing any DLTs at the end of each cohort and for the assessment of the MTD/RP2D.

For final statistical analysis, the number and proportion of subjects in the DLT population who experienced DLT during the Cycle 1 of treatment with MSC2156119J will be presented by dose level. Subject disposition will be reported for each dose level, and subject profiles will be presented.

Listings and graphics of information which is relevant to the primary endpoint will be prepared for the SMC, for the purpose of determination of the MTD/RP2D of MSC2156119J in Asian subjects, according to the content agreed and specified in the SMC's charter.

The MTD/RP2D will be determined as described in Section 7.2.3.

### 9.5.2.2 Statistical Analysis of Primary Endpoint of Phase II

The primary endpoint of Phase II in this trial is TTP based on tumor assessment by an IRC. TTP is defined as the time (in months) from randomization to date of the observation of radiological PD assessed by an IRC. Death without radiological progression date will be censored. In subjects without a progression date or loss to follow-up at time of analysis, the time between the date of randomization and the date of last tumor assessment will be calculated and used as a censored observation in the analysis. In principle, all tumor assessment should be considered to determine and derive the date of radiological progression.

The primary analysis will test the equality of TTP between treatment groups, based on the mITT population, applying two-sided unstratified log-rank test at a significance level of 10%.

The following null-hypothesis is tested:

$$H_0: \lambda_A(t) = \lambda_B(t) \text{ versus } H_1: \lambda_A(t) = \theta \lambda_B(t), \theta \neq 1,$$

where  $\lambda(t)$  represents the hazard at time  $t$  and  $\theta$  the unknown constant of proportionality of hazards in the allocated treatment groups (MSC2156119J and sorafenib).

The HR (including 90% CI) of MSC2156119J compared to sorafenib will be calculated by Cox's proportional hazards model.

Kaplan-Meier survival curves (product-limit estimates) will be presented by treatment arm together with a summary of associated statistics (median survival time, 6-month, 12-month survival rate estimates and estimates for every 6 months thereafter as applicable) including the corresponding two-sided 90% CIs. The CIs for the median will be calculated according to Brookmeyer and Crowley, and CIs for the survival function estimates at above defined time points will be derived directly from the Kaplan-Meier estimates. The estimate of the standard error will be computed using Greenwood's formula. Comparisons of survival rates will be performed from a Z-test using estimates and standard errors derived from the Kaplan-Meier method and Greenwood's formula.

TTP will be further explored considering the ITT population, the PP population and pre-defined subgroups (see Section 9.4).

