
Statistical methods (includes sample size calculation)
	
Statistical analyses of Phase Ib will be carried out in a descriptive manner, whereas Phase II has a confirmatory component when analyzing TTP.
 
Data of Phase Ib will be analyzed after completion of the dose confirmation phase. Primary statistical analyses will be performed using electronic case report form (eCRF) data obtained until a clinical cut-off date in Phase II, which is determined by the date after the required number of events for the primary endpoint has been reported in the primary analysis population, i.e., 40 TTP events for the modified intent-to-treat (mITT) population in Phase II or on 15 August 2017, whichever occurs first. The final statistical analyses for the Phase II study will be performed at approximately 6 months after the last subject is first dosed. Determination of MET status is planned at Molecular Prescreening (Phase Ib retrospectively, Phase II for subject selection); rescoring will be performed as a quality control measure. The mITT population excludes subjects who were randomized but for whom, retrospectively, a c-Met status 1+ or ‘not assessable’ was detected.
 
All data required for the calculation of time-to-event will be taken from eCRF, but randomization strata will be taken as specified in interactive voice/web response service.
 
The DLT population will be used for analysis of Phase Ib. Statistical analyses in Phase Ib will be carried out in a descriptive manner.
 
The mITT population will be primarily used in the analysis of baseline characteristics and efficacy. Analyses on the mITT population will consider subjects’ allocation to treatment groups as randomized.

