### 9.5.3 Analysis of Secondary Endpoints

#### 9.5.3.1 Progression-free Survival

Progression-free survival (assessed by the IRC) time is defined as the time (in months) from randomization to either first observation of progression disease or occurrence of death due to any cause within 84 days of either randomization or the last tumor assessment. If no progression or death is observed at the time of analysis, or if death without previously documented PD is observed after more than 84 days of last tumor assessment without progression, the PFS time will be censored on the date of last tumor assessment or date of randomization, whatever occurs later. The 84-day time window represents the time between 2 scheduled tumor assessments.

Treatment groups will be compared based on mITT population, applying two-sided unstratified log-rank test at a significance level of 10%.

The same survival analysis methods will be employed as for the primary endpoint, PFS will be further explored considering the ITT population, the PP population and pre-defined subgroups (see Section 9.4).

Progression-free survival based on tumor assessment by the investigator will also be analyzed in the same way as described above.

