#### 9.5.3.2 Overall Survival

Overall survival will be measured as the time (in months) between the date of randomization and the date of death. The analysis will be performed on the basis of the ITT principle on the primary analysis population. OS time (in months) is defined as:

$$(\text{date of death or last date known to be alive} - \text{date of randomization} + 1) / 30.4375.$$

For subjects not known to be deceased at time of analysis, the time between date of randomization and date of last contact or date of lost to follow-up will be calculated and used as a censored observation in the analysis. If this date is after the data cut-off, subjects will be censored at the date of data cut-off.

Treatment groups will be compared based on the mITT population, applying two-sided unstratified log-rank test ( $\alpha = 10\%$ ).

OS data will be further explored considering the ITT population, the PP population and predefined subgroups (see Section 9.4).

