### 9.5.3.3 Time-to-symptomatic Progression

Time-to-symptomatic progression is defined as the time (in months) from the date of randomization to the date of deterioration of symptoms assessed by FHSI-8, defined as the total score increase by at least 4 points compared with the baseline value, or deterioration to ECOG PS 4. The analysis will be performed on the basis of the ITT principle on the primary analysis population at time when TTP is statistically analyzed.

Treatment groups will be compared based on the mITT Population, applying two-sided unstratified log-rank test ( $\alpha = 10\%$ ).

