8.1 Primary Analysis

The primary analysis will be conducted when 40 TTP events (confirmed by IRC) reported for mITT population or 15 August 2017, whichever occurs first. Final Analysis

The final statistical analysis is planned to be conducted approximately 6 months after the last subject is first dosed.

Data review meetings will be held prior to database lock for both primary and final analysis.

9 Changes to the Planned Analyses in the Clinical Trial Protocol

The following change was made in the planned analysis between the study protocol and the SAP prior to database lock:

- The following additional criteria added to the definition of PP analysis set:
 - The absence of any clinical important protocol deviations with respect to factors likely to affect the efficacy of treatment.
 - Data review will be held to determine the evaluability of the subjects prior to the database lock.
 - Change the criteria of ‘complete at least 1 cycle of treatment’ to ‘completed at least 80% of the planned dose for at least one cycle, except for patients discontinued due to early death or progression’.

- Kaplan-Meier estimates for TTP will be presented by 2 months, 4 months and every 2 months instead of 6 month, 12 month and every 6 month.

CCI

10 Protocol Deviations and Analysis Sets

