The primary analysis will test the equality of TTP between treatment arms in the randomized part of Phase II, based on the mITT population, applying a two-sided stratified log-rank test at a significance level of $\alpha = 10\%$, taking into account the strata used for randomization, i.e., baseline BCLC stage. IVRS strata other than the eCRF strata will be used.

The following null-hypothesis is tested by the Cox's proportional hazards model stratified according to strata used for randomization:

$$H_0: \lambda_{\text{experimental}}(t) = \lambda_{\text{control}}(t)$$

$$H_1: \lambda_{\text{experimental}}(t) = \theta \lambda_{\text{control}}(t), \theta \neq 1,$$

where $\lambda(t)$ represents the hazard at time t and θ the unknown constant of proportionality of hazards in the allocated treatment groups in the randomized part. Ties will be handled by replacing the proportional hazards model by the discrete logistic model. With this ties option the Score-test in the Cox's proportional hazards model is identical to the log-rank test:

```
proc phreg data=xxx;
    strata BCLC;
    model TTE*TTE_censor(1) = treatment / ties = discrete rl;
    ods output globaltests=logRank_TTE (where=(test='Score'));
    parameterestimates = HR_TTE ;
run ;
Where:
TTE_censor = 1 if censored, 0 otherwise
Treatment = 1 if in experimental arm, =0 if in control arm
TTE      = Time to event variable, for primary analysis it is TTP by IRC.
```

The hazard ratio θ and 90% CIs of Tepotinib compared to sorafenib will be calculated by Cox's proportional hazards model stratified by baseline BCLC (stage B vs stage C).

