Kaplan-Meier curves (product-limit estimates) will be presented by treatment arm together with a summary of associated statistics (25th quintile, median and 75th quintile survival time, 2-months, 4-months KM estimates and estimates for every 2 months thereafter as applicable) including the corresponding two-sided 90% CIs. The CIs for the median will be calculated according to Brookmeyer and Crowley (1982), and CIs for the survival function estimates at above defined time points will be derived from the Kaplan-Meier estimates using the log-log transformation (CONFTYPE=LOGLOG in SAS PROC LIFETEST). The estimate of the standard error will be computed using Greenwood's formula. Comparisons of survival rates will be performed from a Z-test using estimates and standard errors derived from the Kaplan-Meier method and Greenwood's formula. SAS procedure LIFETEST will be used to obtain Kaplan-Meier estimates and plots.

Sensitivity analysis

An un-stratified Cox model will be fitted, by which the hazard ratio θ , the 90% CIs and p-value will be calculated.

Multivariate analysis will be performed with a stepwise selection to assess the effect of predefined baseline covariates, which are the subgroup variables in Section 10.2 (except for baseline tumor HGF and baseline biomarker variables measured in plasma).

The model selection is performed without fitting the treatment group in the proportional hazards model. The values 0.15 and 0.40 will be used as the p-value for entry into the model inclusion and p-value for staying in the model, respectively exclusion criteria.

```
proc phreg data=Eff_mITT ;
    class all-subgroup variables;
    strata BCLC;
    model TTE*censor(1)= all-subgroup variables /ties=discrete rl selection=stepwise
    slentry=0.15 slstay=0.40 details;
    ods output globaltests=logRank(where=(test='Score')) parameterestimates=HR;
run ;
Where:
slentry= boundary for p-value of Score test for inclusion, other values than 0.15 can be
considered
slstay= boundary for p-value of Wald test for exclusion, other values than 0.40 can be considered
```

Once the selection procedure is finalized the model will be refitted with the strata and the treatment group, plus the selected covariates.

```
proc phreg data=xxx;
    strata BCLC;
    class all-selected-covariates;
    model TTE*TTE_censor(1) = treatment all-selected-covariates / ties = discrete rl;
    ods output globaltests=logRank_TTE (where=(test='Score'))
    parameterestimates = HR_TTE ;
run ;
Where:

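### Protocol and Phase II SAP name different log-rank tests for TTP, PFS, OS and TTSP; the SAP also misnames the response strata and omits the promised ITT analyses

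*Protocol*

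**What the plan says.** **Time-to-event tests.** Protocol 9.5.2.2 compares TTP by IRC in the mITT set by "applying two-sided unstratified log-rank test at a significance level of 10"%. Sections 9.5.3.1 to 9.5.3.3 repeat the unstratified test for PFS, OS and TTSP; for OS the wording is "Treatment groups will be compared based on the mITT population, applying two-sided unstratified log-rank test". Phase II SAP 16.1 keeps the endpoint, population and level but is "applying a two-sided stratified log-rank test at a significance level of" 10%, with BCLC stage taken from IVRS. The hazard ratio comes from a Cox model stratified the same way. Under sensitivity analysis it adds: "An un-stratified Cox model will be fitted". SAP 16.2.1, 16.2.3 and 16.2.5 carry the primary methods over to PFS, OS and TTSP.

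**Declared changes.** SAP section 9 opens with "The following change was made in the planned analysis between the study protocol and the SAP prior to database lock". Its visible items are the per-protocol criteria and the Kaplan-Meier time points.

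**Response.** Protocol 9.5.3.4 uses Fisher's exact test for objective response and disease control. SAP 16.2.6 uses Cochran-Mantel-Haenszel for objective response, describes the randomization strata as 'type of Met+', and gives disease control an interval but no test.

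**Analysis sets.** Protocol 9.5.2.2, 9.5.3.1 and 9.5.3.2 promise TTP, PFS and OS in the ITT set as well. SAP 16.1 and 16.2 name only mITT and, conditionally, PP.

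**Power.** Protocol 9.1 and SAP section 7 give an initial plan of 100 events for 80% power. Both then move to 40 IRC events or 15 August 2017, whichever is first, without restating power.

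**The concern.** A trial with a confirmatory component (Protocol 9.5.1) should have one primary p-value that can be identified from its governing documents. Here two are on offer for the same endpoint, set and level, and in some data sets they fall on opposite sides of 10%. A programmer following the SAP's response section literally would stratify on a factor that was not used for randomization.

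The ITT gap bears on interpretation. The mITT set removes subjects whose c-Met status is rescored as 1+ or 'not assessable' after randomization. Comparing all randomized subjects is the direct check on that exclusion, and the SAP no longer plans it.

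Finally, a reader who sees only the 80% figure may take a non-significant result at 40 events as stronger evidence of no effect than it is.

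**Working it through.** **1. The texts side by side**

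| Item | Protocol | Phase II SAP |
|---|---|---|
| TTP, PFS, OS, TTSP test | Unstratified log-rank (9.5.2.2, 9.5.3.1–9.5.3.3) | Log-rank stratified by BCLC stage (16.1, carried to 16.2.1, 16.2.3, 16.2.5) |
| Randomization stratum | BCLC stage only (9.2) | BCLC stage (7, 16.1); 'type of Met+' (16.2.6) |
| Objective response test | Fisher's exact (9.5.3.4) | Cochran-Mantel-Haenszel (16.2.6) |
| Disease control test | Fisher's exact (9.5.3.4) | None named (16.2.6) |
| ITT for TTP, PFS, OS | Yes | No ITT column in Table 1 (10.2); not named in 16.1 or 16.2 |
| ITT c-Met subgroup | Covers change to 1+ or 'not assessable' (9.4) | Levels 1+, 2+, 3+ only (10.2) |

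The SAP's stratum for response contradicts its own sections 7 and 16.1. The one remaining ITT item is a subgroup Cox model, run only if there are more than 10 subjects per group. It has no level for subjects rescored 'not assessable'. So no visible efficacy comparison covers everyone randomized.

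**2. Does the choice of log-rank test matter?** Simulation, 8,000 trials per setting: 90 subjects, cut at the 40th event, sorafenib median 2.8 months. Assumed: 12-month accrual and 17.4% drop-out (both from the 140-subject plan), blocks of 4 within stage, stage B share 10–40%, stage C versus B hazard ratio 1–2.

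| True HR | Unstratified rejects | Stratified rejects | Decisions differ |
|---|---|---|---|
| 1.0 | 9.5–11.0% | 10.0–11.1% | 2.7–4.9% |
| 0.6 | 45.5–48.1% | 46.4–47.6% | 4.8–8.2% |

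A second simulation without drop-out (10,000 trials per setting, stage B 15–30%) gave differing decisions in 2.9–4.0% and 4.9–7.7%. Placing progression on the 6-weekly scan grid left these much the same (about 2.5–4% and 4.6–8%). A stage hazard ratio of 3, outside the main range, raises the figure at HR 0.6 to 6.6–11.4%.

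**3. Power.** Inputs from Protocol 9.1: HR 0.6, two-sided 10% (z = 1.645), 80% power (z = 0.842), 1:1.

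- Planned events, Freedman: (1.6/0.4)² × (1.645 + 0.842)² = 98.9. Schoenfeld: 4 × (1.645 + 0.842)² / (ln 0.6)² = 94.8. The stated 100 is reproduced.
- Planned subjects: with 12 months' accrual and 6 months' follow-up the average event probability is 0.868. Then 100 / 0.868 / (1 − 0.174) = 139.5, against 140 stated.
- At 40 events, Freedman: Φ(√40 × 0.4/1.6 − 1.645) = 47.5%. Schoenfeld: Φ(√40/2 × |ln 0.6| − 1.645) = 48.8%. Significance needs an observed HR of at most exp(−2 × 1.645/√40) = 0.594.
- If the date comes first with 30 events (assumed): 39.1% and 40.3%.
- Final analysis about 6 months after the last first dose: keeping the planned accrual and drop-out (hazard 0.0446 per month, event probability 0.741), 90 × 0.741 = 66.7 events. The same formulas give 65.4% and 67.0%.

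**The case against.** The strongest reply is that the SAP leaves no real ambiguity. Protocol 9.5.1 defers detail to the SAP, which ranks the stratified test as primary and the unstratified model as sensitivity, so both will be reported. Both tests are valid with practically equal power, and the IRC reads images blinded (Protocol 2.2.3). This stands, and limits the point to traceability.

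Some stronger readings are tempting, but the documents do not support them.

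- *The test was left open, or switched after results.* SAP section 4 dates V1.0 to 13 July 2017, before the latest possible cut-off of 15 August 2017, and the V1.1 entry lists no change of test.
- *SAP section 9 conceals a change.* A redacted block follows its list. The SAP also appears to follow different protocol wording: its section 6 continues data collection to the end-of-treatment assessment, where Protocol 6.5 says the end of the trial. It also admits subjects already in prescreening, where the protocol requires consent before 15 August 2017. If the SAP matched its source version, it had nothing to declare.
- *The protocol synopsis already prescribes stratification.* It says "randomization strata will be taken as specified in interactive voice/web response service". That gives the source of the values, not the test; BCLC stage is also a subgroup factor.
- *The 80% power claim is false.* It is labelled as initial planning and it reproduces.

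It is also fair that SAP 16.2.6 plans an unadjusted odds ratio with its 90% interval, so only Fisher's p-value is lost. No document says how many subjects rescoring will remove, so the effect of the missing ITT analysis cannot be sized.

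**Conclusion.** The conflict between the two documents is real and should be fixed, but it is a reconciliation defect rather than an error-rate problem. The two tests would lead to different decisions in roughly 3–5% of trials under no effect and 5–8% at HR 0.6. Those ranges rest on the assumed stage mix, a stage hazard ratio of 1–2, and accrual and drop-out borrowed from the 140-subject design.

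Two items are wrong or missing on the text alone, without any assumption: the 'type of Met+' strata in SAP 16.2.6, and the loss of the ITT analyses of TTP, PFS and OS, including the 'not assessable' subjects.

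Power is a supporting point. It is about 47–49% at 40 events for HR 0.6, lower if the date comes first, and about 65–67% at the final analysis if about 67 events accrue. Neither document gives that later analysis a defined test role for TTP.

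**What to change.** 1. Name the log-rank test stratified by IVRS BCLC stage as the single primary TTP test in Protocol 9.5.2.2 and SAP 16.1, with the unstratified test as sensitivity, and likewise for PFS, OS and TTSP. Do this by protocol amendment or as a declared change in SAP section 9.
2. In SAP 16.2.6 correct the strata to BCLC stage. Name one response test in both documents, for example Cochran-Mantel-Haenszel by BCLC stage with Fisher's exact as sensitivity, and say whether disease control is tested.
3. Restore the ITT analyses of TTP, PFS and OS by the primary method, add an ITT column to Table 1 in SAP 10.2, and add a 'not assessable' level to the ITT c-Met subgroup.
4. Beside the initial 80%, state the power at 40 events and that it falls if the date comes first. State the role of the final analysis and its power, with the assumed event count.

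Cost: a protocol amendment, which may need authority and ethics submission (Protocol 11.5), or a declared deviation; a few extra tables; and a less favourable stated power. No additional subjects or follow-up are needed.

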### 9.5.3 Analysis of Secondary Endpoints

#### 9.5.3.1 Progression-free Survival

Progression-free survival (assessed by the IRC) time is defined as the time (in months) from randomization to either first observation of progression disease or occurrence of death due to any cause within 84 days of either randomization or the last tumor assessment. If no progression or death is observed at the time of analysis, or if death without previously documented PD is observed after more than 84 days of last tumor assessment without progression, the PFS time will be censored on the date of last tumor assessment or date of randomization, whatever occurs later. The 84-day time window represents the time between 2 scheduled tumor assessments.

Treatment groups will be compared based on mITT population, applying two-sided unstratified log-rank test at a significance level of 10%.

The same survival analysis methods will be employed as for the primary endpoint, PFS will be further explored considering the ITT population, the PP population and pre-defined subgroups (see Section 9.4).

Progression-free survival based on tumor assessment by the investigator will also be analyzed in the same way as described above.

